### **5.6.4        Documentation of Prior and Concomitant Medication Use**

All concomitant medications (including prescription medications and over-the-counter preparations) used by the participant from date of ICF signing, during the study, and at the final study visit will be documented and recorded in the eCRF.

## **6 STUDY PROCEDURES AND VISITS**

### **6.1 INFORMED CONSENT**

Written informed consent must be obtained from participants by the Investigator or delegated clinician/staff member before any study-specific procedures are performed. See Section [12.2](#) for details on consent.

### **6.2 STUDY PROCEDURES**

The Schedule of Activities (SoA) summarizes the frequency and timing of efficacy, safety, and immunogenicity assessments applicable to this study.

The diagnosis of idiopathic PD will be made before any other screening procedure takes place. During screening, assessments that are not part of the study entry criteria will be performed after the participant has qualified to enroll in the study (as per footnote “p” of the SoA [[Table 1](#)]).

All participants will be provided with an emergency card on enrollment to the study to enable 24-hour contact with study Investigators.

Participants randomly assigned to immediate treatment with AAV-GAD will be scheduled for surgery and complete the full battery of visits through the Week 26 visit (as described in the SoA), and then enter the long-term follow-up MGT-GAD-026 study.

Participants randomly assigned to sham surgery will follow the same visit schedule during the first 6 months, and then enroll in the long-term follow-up MGT-GAD-026 study, in which these participants will be offered treatment with AAV-GAD. The Week 26 visit of this study will serve as the Baseline visit of MGT-GAD-026.

Any medical condition already present at Screening should be recorded as medical history and not be reported as an AE unless the medical condition or signs or symptoms present at screening change in severity, frequency, or seriousness at any time during the study. In such a case, it should be reported as an AE.

The Week 19 visit is a telephone visit for assessment of AEs, changes in control of Parkinsonism, and other neurological events. The following actions must be taken if a participant fails to answer or return phone calls:

- The study-site personnel must attempt to contact the participant to reschedule the missed telephone visit as soon as possible.
- The Investigator or designee must make every reasonable effort to regain contact with the participant (where possible, 3 telephone calls, emails, fax).
- Should the participant continue to be unreachable, they will be considered to have missed the telephone visit.

During visits that include the UPDRS assessment, the MDS-UPDRS Part 3 “off” state assessment should preferably be performed before any other assessments or questionnaires. Site staff are to confirm that the last dose of dopaminergic medication(s) was taken by the participant at least 12 hours before performing the MDS-UPDRS Part 3 “off” state assessment (also see Section 7.2).

For the other assessment tools, the following order is recommended:

1. HVLT-R (10 min + 20-25 min delay\*)
2. Trail Making Test (10 min)
3. Color-word interference (10 min)
4. Digit Span Test (5 min)
5. \*HVLT-R delayed memory (continued from 1, above, after planned delay)
6. Verbal fluency test (10 min)
7. All other questionnaires

Additional serum or urine pregnancy tests may be performed, as determined necessary by the Investigator or required by local regulation, to establish the absence of pregnancy at any time during the participation in the study. Similarly, unscheduled clinical chemistry examinations will be permitted as required to manage emerging issues.

### **6.3           EARLY TERMINATION VISIT AND WITHDRAWAL PROCEDURES**

The end-of-treatment visit for participants completing the study is the Week 26 visit.

If a participant who received surgery withdraws early, they will be encouraged to maintain contact with the Investigator and allow reporting to the sponsor of follow-up MRI and clinical features related to Parkinson's disease and other neurological problems. Every effort should be made to complete the full panel of assessments scheduled for the Week 26 Visit.

If a participant discontinues (for any reason) the study after surgery on Day 1, all assessments scheduled for the Week 26 Visit should be completed.

In the case of a participant lost to follow-up, attempts to contact the participant must be made and documented in the participant's medical records.

## 7 EFFICACY ASSESSMENTS

### 7.1 FDG-PET

FDG-PET scans will be performed per site standards to assess patient's eligibility and evaluate the abnormalities in brain network activity and biological changes in brain function.

Scans will also be evaluated for PDRP and GADRP at baseline and at 6 months after study drug administration as an exploratory evaluation for potential correlates of activity.

PDRP score is a z-scale unit score of FDG-PET brain network pattern.

GADRP score is a z-scale unit score of FDG-PET brain network pattern associated with response to AAV-GAD therapy, involving the generation of new polysynaptic functional pathways linking the STN to the motor cortical regions.

FDG-PET scans will be collected for centralized reading by an independent specialist.

### 7.2 QUESTIONNAIRES AND SCALES

The following assessment tools will be used in this study:

- Columbia Suicide severity rating scale: a measure assessed by the Investigator or a qualified member of her/his team (e.g., a neurologist), used to identify and assess individuals at risk for suicide.
- Beck Depression Inventory-II: a 21-item self-report inventory measuring the severity of depression in adolescents and adults
- Beck Anxiety Inventory: a 21-item self-report inventory measuring the severity of anxiety in adolescents and adults
- Clinical Global Impression-Severity: a 7-point scale completed by the Investigator or a qualified member of her/his team (e.g., a neurologist), to rate the severity of the participant's illness at the time of assessment, relative to her/his baseline state (prior to the surgery)
- Clinical Global Impression-Improvement: a 7-point scale completed by the Investigator or a qualified member of her/his team (e.g., a neurologist) to assess how much the participant's illness has improved or worsened relative to her/his baseline state (prior to the surgery)
- EuroQol-5 Dimensions-5 Levels Survey comprises five dimensions: mobility, self-care, usual activities, pain/discomfort and anxiety/depression. Each dimension has 5 levels: no problems, slight problems, moderate problems, severe problems and extreme problems. The participant is asked to indicate his/her health state by ticking the box next to the most appropriate statement in each of the five dimensions. This decision results in a 1-digit number that expresses the level selected for that dimension. The digits for the five dimensions can be combined into a 5-digit number that describes the patient's health state.

- Montreal Cognitive Assessment: a brief cognitive screening task assessment administered by the Investigator or a qualified member of her/his team (e.g., a neuropsychologist) of different cognitive abilities such as visuospatial skills, executive function, memory, language and attention.
- Parkinson's Disease Questionnaire-39 Scale: a 39-item questionnaire completed by participants that measures health status and quality of life
- Parkinson's Disease Sleep Scale-2: a 15-item scale completed by participants to self-rate and quantify the level of sleep disruption being experienced
- Unified Dyskinesia Rating Scale: a scale formatted as a questionnaire for the participant and completed by the Investigator or a qualified member of her/his team (e.g., a neurologist), used to evaluate the involuntary movements that can be associated with long-term treatment with dopaminergic medication
- MDS-Unified Parkinson's Disease Rating Scale Part 1 (Non-Motor Experiences of Daily Living), Part 2 (motor experiences of daily living), Part 3 (motor examination) and Part 4 (motor complications). Part 1 has two components: 1A concerns a number of behaviors that are assessed by the Investigator or a qualified member of her/his team (e.g., a neurologist) with all pertinent information from participants and caregivers, and 1B will be completed by the participant with or without the aid of the caregiver, but independently of the Investigator. Part 2 is designed to be a self-administered questionnaire like Part 1B. Part 3 will be completed by the Investigator or a qualified member of her/his team (e.g., a neurologist) and has instructions for the Investigator to give or demonstrate to the participant. Part 4 integrates patient-derived information with the Investigator's clinical observations and judgments and will be completed by the Investigator or a qualified member of her/his team (e.g., a neurologist).

The MDS-UPDRS Part 3 will first be completed while in the “off” state. “Off” state scores will be obtained after at least 12 hours of holding dopaminergic medication. Once this assessment is completed, participants are to take their usual medications for Parkinson's disease. “On” state evaluations will be assessed when participants and Investigators agree that the participant is in a typical “on” state (as a guidance, the “on” state is expected to be achieved approximately 2 hours after taking medication(s) for Parkinson's disease). Participants may take additional levodopa (in addition to their usual dose) if needed to achieve the “on” state.

- Revised Hopkins Verbal Learning Test (HVLT-R) is a test administered by the Investigator or a qualified member of her/his team (e.g., a neuropsychologist), assessing verbal memory. Participants are presented with a list of words over repeated learning trials and are required to recall words from the list immediately and after a delay of 20-25 minutes and complete a yes-no delayed recognition task. The HVLT-R also provides 6 alternate forms in order to reduce the effects of practice and will be administered during each session.
- Stroop Color and Word Test (DKEFS version) is a test administered by the Investigator or a qualified member of her/his team (e.g., a neuropsychologist), measuring processing speed and

executive functioning. There are 4 parts. Participants are required to read printed color names as fast as possible (Part 1), and name color patches as fast as possible (Part 2). To assess executive functioning, and specifically cognitive inhibition, participants are then required to name the ink color of printed color names, avoiding the 'read' the printed work. In the 4th part, participants are required to do the same as in Part 3 unless the word is presented in a box, and in these instances, they must read the word instead of naming the color.

- Trail Making Test (TMT) (DKEFS version) is a paper-and-pencil test administered by the Investigator or a qualified member of her/his team (e.g., a neuropsychologist), measuring processing speed and executive functioning. There are 4 trials to complete including a cancellation task (i.e., cross-out targets as fast as possible), simple tracking tasks requiring participants to connect numbers with a line as fast as possible, connect letters in order, and lastly, a more complex task requiring them to alternate between numbers and letters in sequences.
- Verbal fluency Test (DKEFS version) is a verbal fluency test administered by the Investigator or a qualified member of her/his team (e.g., a neuropsychologist), measuring executive function and language abilities. Participants are required to generate as many words as possible aloud within a one-minute period following letter cues (3 trials) and category cues (3 trials).
- Digit Span test (part of Weschler Memory and Weschler scales) is a test administered by the Investigator or a qualified member of her/his team (e.g., a neuropsychologist), measuring attention and working memory span. Participants are required to repeat strings of digits of increasing length in the same order as well as in reverse order.

To the extent possible, all questionnaires to be used in repeated assessments should be administered by the same rater (Investigator, neuropsychologist, or neurologist, as applicable).

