**Exploratory activity assessments:**

Assessments of potential activity of AAV-GAD will include the MDS-UPDRS, Parkinson's disease-related pattern (PDRP), glutamic acid decarboxylase-related pattern (GADRP), MDS-Unified Dyskinesia Rating Scale, Montreal Cognitive Assessment, Parkinson's Disease Sleep Scale-2, Hauser Patient Diary,

Parkinson's Disease Questionnaire-39 Scale, EuroQol-5 Dimensions-5 Levels Survey, Clinical Global Impression-Severity, Clinical Global Impression-Improvement, Beck Depression Inventory-II, Beck Anxiety Inventory, Revised Hopkins Verbal Learning Test (HVLT-R), Stroop Color and Word Test (DKEFS version), Trail Making Test (TMT), Verbal fluency Test (DKEFS version), Digit Span Test, and levodopa dose and levodopa equivalent daily dose.

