Parkinson's Disease Questionnaire-39 Scale	X p									X
Parkinson's Disease Sleep Scale-2	X p									X
Columbia-Suicide Severity Rating Scale	X p						X	X		X
EuroQol-5 Dimensions-5 Levels Survey	X p									X
Clinical Global Impression-Severity	X p									X
Clinical Global Impression-Improvement										X
Randomization	X q									
Surgery and related procedures			X							
Stereotactic imaging following frame placement (CT or MRI)			X							
Limited-cut CT at catheter tip to confirm localization following infusion (AAV-GAD groups only)			X							
Non-contrast CT of head within 24 hours after catheter removal (AAV-GAD groups only)				X						
Sham limited-cut CT at catheter tip to confirm localization following infusion (SHAM group only)			X							
Sham non-contrast CT of head within 24 hours after catheter removal (SHAM group only)				X						
Study drug administration			X							
Removal of catheter			X							
Removal of sutures and burr hole site assessment						X				
Anti-GAD and anti-AAV2 antibody evaluation (humoral immune response)		X					X	X		X

Study Day/Month	Screening		Surgery/ Hospital		UV	Day 15 ±2 days	Day 29 ±3 days	Week 12 ±7 days	Week 19 a ±7 days	Week 26/EW ±7 days
	Day -40 to Day -8	Day -7 to Day -3	Day 1	Day 2						
Hauser Patient Diary review		X				X r		X r		X r
Check on control of Parkinsonism, and other neurological events									X	

Note: If, despite all efforts to encourage the participant to continue in the study, the participant withdraws consent after Day 1, every effort should be made to complete the full panel of assessments scheduled for the Week 26 visit.

During visits that include the MDS-UPDRS assessment, the MDS-UPDRS Part 3 “off” state assessment should preferably be performed before any other assessments or questionnaires.

- a. Telephone visit. Participants will be contacted by telephone for assessment of AEs, changes in control of Parkinsonism, and other neurological events.
- b. Assessments preferably to be performed between Day -40 and Day -21.
- c. MRI and FDG-PET scans done for surgical screening will be used as baseline assessments. Due to the retention of the nylon/titanium cranial anchor base above the skull as a burr hole cover following removal of the infusion system, the specific MRI conditions detailed in the IFU must be taken into account for all post-surgical MRI scans.

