- d. If an MRI of the head is done at screening, the MRI for presurgical planning does not need to be done.
- e. The diagnosis of idiopathic PD will be made before any other screening procedure will take place.
- f. Demographics will include sex, age, race and ethnicity.
- g. Prior and concomitant medications will be recorded from date of informed consent form (ICF) signature till the final study visit on electronic case report form (eCRF). Changes in concomitant medications should be recorded before and after surgery.
- h. Participants will be contacted by telephone on Day 7 or 8 (6 or 7 days after study drug administration) for assessment of AEs.
- i. “Off” state scores will be obtained after at least 12 hours of holding dopaminergic medication.
- j. Participants may take additional levodopa (in addition to their usual dose) if needed to achieve the “on” state.
- k. Prior to the surgery
- l. Vital sign measurements: temperature, heart rate, respiratory rate, and blood pressure will be recorded before surgery, approximately every 30 minutes for at least the first 4 hours after start of infusion (this can be prolonged in 30-minute intervals if the infusion takes longer than 4 hours), and then at approximately 8 and 12 hours after the start of infusion. Of note, the participant may be transferred to an inpatient hospital service for the assessment of vital signs between 4 hours and 12 hours after start of infusion. Height will be measured at screening, whereas weight will be measured at both screening and Week 26 visits.
- m. Coagulation parameters will not be evaluated.
- n. Serum or urine pregnancy tests may be performed, as determined necessary by the Investigator or required by local regulation, to establish the absence of pregnancy at any time during the participation in the study.
- o. Inform the participant that the Hauser Patient Diary should be completed twice per week (on 2 non-sequential days) for 3 consecutive weeks prior to the second screening visit (i.e., the Day -7 to Day -3 visit). After baseline, the participant should complete the Hauser Patient Diary on 2 non-sequential days in the week prior to Day 15, and Week 12, and Week 26.
- p. Assessment only to be performed after the participant has qualified to enroll in the study.
- q. Randomization will occur after all inclusion and exclusion criteria have been met and surgery is scheduled.

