## **10.1.4 Analysis of Efficacy**

### **10.1.4.1 Exploratory Efficacy Endpoints**

The exploratory efficacy analyses will be performed at Weeks 12 and 26.

Descriptive statistics will be presented for efficacy endpoints. Differences between the individual and pooled (when appropriate) AAV-GAD groups and the sham group in mean change from baseline to Weeks 12 and 26 will be compared for each of the endpoints.

Additional sensitivity analyses will be described in the SAP.

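### CGI-Severity is defined against the participant's own pre-surgery state, which conflicts with its scheduled pre-surgery rating and, read literally, makes it a second CGI-Improvement

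*Combined protocol and SAP*

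**What the plan says.** Four places in the protocol bear on this.

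- **Definition of CGI-Severity (Section 7.2).** A 7-point scale, completed by the investigator or a qualified team member, "to rate the severity of the participant's illness at the time of assessment, relative to her/his baseline state (prior to the surgery").
- **Definition of CGI-Improvement (Section 7.2, next bullet).** A 7-point scale with the same kind of rater, "to assess how much the participant's illness has improved or worsened relative to her/his baseline state (prior to the surgery").
- **Timing (Table 1, Schedule of Activities).** The row "Clinical Global Impression-Severity" is marked at screening and at Week 26/early withdrawal. The row "Clinical Global Impression-Improvement" is marked at Week 26/early withdrawal only. The screening mark carries footnote p: "Assessment only to be performed after the participant has qualified to enroll in the study". Neither scale is rated at Week 12.
- **Analysis (Section 10.1.4.1, and the matching synopsis paragraph).** AAV-GAD and sham differences "in mean change from baseline to Weeks 12 and 26 will be compared for each of the endpoints".

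The synopsis lists the two scales as separate activity assessments: "EuroQol-5 Dimensions-5 Levels Survey, Clinical Global Impression-Severity, Clinical Global Impression-Improvement, Beck Depression Inventory-II". Section 10.1.1 limits formal hypothesis testing to MDS-UPDRS Part 3 and GADRP.

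**The concern.** A scale that is rated before and after treatment and analysed as a change needs a first rating that carries information about the participant. The schedule treats CGI-Severity as such a scale. The definition does not: it tells the rater to judge current severity against the pre-surgery state, and at screening the current state is the pre-surgery state.

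What is at stake is whether the trial collects a clinician rating of how ill each participant is, as distinct from how much each has changed. This has to be settled when the rating is made. A SAP can choose how to analyse the scores, but it cannot recover an absolute severity rating that was never recorded.

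**Working it through.** The plan gives no figure to reproduce here, and no sample size or power calculation is involved. The check sets the definition, the schedule and the analysis rule side by side.

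**Notation.** Let B be the participant's pre-surgery state and S(t) the state at visit t. Let f be the 7-point rating of one state relative to another, and g an absolute 7-point rating of a single state.

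**1. Literal reading, all raters.** CGI-Severity at visit t is f(S(t) relative to B).
- Screening: S = B, so the rating is f(B relative to B) = c, the same value for every participant, with no variation between participants.
- Week 26: the rating is f(S(26) relative to B).
- Change: f(S(26) relative to B) − c.

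CGI-Improvement at Week 26 is also a rating of S(26) relative to B. The two scales therefore measure the same thing, at the same visit, with the same kind of rater. The two numbers need not be identical, because the protocol text does not give the anchors of either scale.

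**2. Between-group comparison under the literal reading.** For an AAV-GAD group and sham,

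(mean of f in AAV-GAD − c) − (mean of f in sham − c) = mean of f in AAV-GAD − mean of f in sham.

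The constant cancels. What is left is a valid comparison of rated change, but it carries the name of severity and adds no separate construct to CGI-Improvement. The individual change score equals the Week 26 rating only if c = 0, which the documents do not establish.

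**3. Absolute reading, all raters.** CGI-Severity at visit t is g(S(t)). The screening value g(B) can differ between participants, the change is g(S(26)) − g(B), and the endpoint is distinct from CGI-Improvement. This is the reading that fits the schedule.

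**4. Mixed readings.** Some participants contribute f(S(26) relative to B) − c and others g(S(26)) − g(B). If one participant is rated absolutely at screening and relatively at Week 26, the difference is f(S(26) relative to B) − g(B), which is neither a change in severity nor a rating of change. A group mean over such scores has no single meaning. With 5, 5 and 4 participants planned per group and approximately 5 sites, a few raters who read the sentence differently could affect a large share of a group.

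**Result.** The definition and the screening rating are consistent only under the absolute reading, and the definition's own reference clause points away from it.

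**The case against.** The best defence is that the sentence is a one-line description of a tool and that an absolute rating was probably meant. It speaks of severity when the assessment is made, the scale is named for severity, and the schedule gives it a screening rating while giving CGI-Improvement none. The form that raters complete is not in the documents and may carry absolute anchors. Section 7.2 also asks that repeated questionnaires be given by the same rater where possible, which limits mixed readings within a participant. All of this stands, and it is why the endpoint may turn out usable. It does not remove the conflict: no visible text supplies absolute anchors, the one written instruction says otherwise, and using the same rater over time does not give different sites a common definition.

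A reader might go further and infer that the CGI-Severity comparison is lost or uninterpretable. The documents do not support that. Under uniform literal use it is redundant and mislabelled, but it can be interpreted; under uniform absolute use it is intact. Only mixed use damages it, and nothing in the protocol shows that mixed use will occur.

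A reader might also infer that CGI-Improvement has been given an analysis that cannot be done, since it has no baseline to subtract. That over-reads a generic sentence, which also names Week 12 although neither CGI scale is rated then. CGI-Improvement is already a rating of change, so comparing the Week 26 rating is its natural application. The Section 2 endpoint table and any SAP wording on this endpoint are not visible in the text reviewed, and the synopsis paragraph is followed by a redaction, so a specific rule may exist there.

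**Conclusion.** Wrong as written, of minor severity. The Section 7.2 definition of CGI-Severity conflicts with its pre-surgery rating in the Schedule of Activities and with the general change-from-baseline comparison. Followed literally, it yields a constant at screening and a Week 26 change that duplicates CGI-Improvement. Read differently by different raters, it yields scores that are not comparable.

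The reach is one exploratory endpoint, at Week 26 only. It is not formally tested, and the primary safety objective does not depend on it.

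Two assumptions carry the conclusion. The first is that raters work from the Section 7.2 text; if their form has absolute anchors and all of them use it, the ratings are sound and only the protocol wording is at fault. The second is that the general change-from-baseline rule applies to CGI-Severity, which cannot be confirmed without the endpoint table. The conflict between definition and schedule does not need the second assumption.

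**What to change.** In Section 7.2, delete from the CGI-Severity bullet the clause that ties the rating to the pre-surgery state, so that it is an absolute rating of severity at each visit. Leave the CGI-Improvement bullet unchanged. Send raters a short reminder that CGI-Severity is absolute and CGI-Improvement is relative to the pre-surgery state.

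As a clarification only, add to Section 10.1.4.1 that CGI-Improvement, having no baseline rating, is compared as the Week 26 rating itself. Omit this if the endpoint table or the SAP already says so.

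The cost is one clause removed, at most one sentence added, and one rater communication. No visit, assessment or procedure changes.
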